PROTOCOL TITLE 'Incidence of Cervical Cancer in HPV-positive Women with Low-grade Cytological Abnormalities'

Protocol ID	2025-03
Short title	Incidence of Cervical Cancer in HPV-positive Women with Low-grade Cytological Abnormalities
Version	2.3
Date	November 2025

TABLE OF CONTENTS

1. INTRODUCTION AND RATIONALE	7
2. OBJECTIVES	8
3. STUDY DESIGN	9
4. STUDY POPULATION	9
4.1 Population (base)	9
4.2 Inclusion criteria	9
4.3 Exclusion criteria	9
5. METHODS	10
5.1 Study parameters/endpoints	10
5.1.1 Main study parameter/endpoint	10
5.1.2 Secondary study parameters/endpoints	10
5.1.3 Other study parameters	10
6. STATISTICAL ANALYSIS	11
6.1 Primary study parameter(s)	11
6.2 Secondary study parameter(s)	11
6.3 Other study parameters	11
7. ETHICAL CONSIDERATIONS	13
7.1 Regulation statement	13
7.2 Recruitment and consent	13
8. ADMINISTRATIVE ASPECTS, MONITORING AND PUBLICATION	14
8.1 Handling and storage of data and documents	14
8.2 Amendments	14
8.3 Public disclosure and publication policy	14
9. REFERENCES	15

LIST OF ABBREVIATIONS AND RELEVANT DEFINITIONS

AGC: Atypical Glandular Cells of Endocervical Origin

ASC-US: Atypical Squamous Cells of Undetermined Significance

CIN: Cervical Intraepithelial Neoplasia

HPV: Human Papillomavirus

IQR: Interquartile Range

LSIL: Low-grade Squamous Intraepithelial Lesion

NILM: Negative for Intraepithelial Lesion or Malignancy

PALGA: Dutch nationwide pathology databank

SD: Standard Deviation

SUMMARY

Rationale:

Since 2017, the Dutch cervical cancer screening program has adopted human papillomavirus (HPV) testing with referral for colposcopy in all HPV-positive women with cytological abnormalities. However, most low-grade abnormalities — atypical squamous cells of undetermined significance (ASC-US), atypical glandular cells of endocervical origin (AGC), and low-grade squamous intraepithelial lesions (LSIL) — regress spontaneously, which may result in overdiagnosis, overtreatment, and unnecessary pressure on the healthcare system. To evaluate whether follow-up intensity can be safely reduced, it is important to assess the actual cancer risk in this subgroup and compare it with the risk in women with stable negative for intraepithelial lesion or malignancy (NILM) cytology after one year, who are currently returned to the screening program.

Objective:

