1. INTRODUCTION AND RATIONALE

Cervical cancer is the fourth most common cancer among women worldwide and remains a leading cause of cancer-related mortality.[1] Prevention is largely possible through organized screening programs. These typically involve the collection of cervical samples to test for the presence of human papillomavirus HPV and to detect cytological abnormalities suggestive of (pre)cancerous lesions.[2,3] Implementation of such screening programs has been associated with a reduction in the incidence of cervical cancer.[4,5]

In the Netherlands, the national cervical cancer screening program invites women aged 30 to 60 every five years.[6] Since 2017, the Dutch program has shifted from a cytology-based to primary HPV based screening, according to international guidelines.[6–8] This shift aims to improve early detection of high-grade lesions and reduce cervical cancer incidence, as over 90% of women with cervical cancer are HPV-positive.[9] Women who test HPV-positive undergo follow-up cytology, and those with abnormal cytology—regardless of grade— are referred for colposcopy.

However, a considerable proportion of HPV-positive women present with low-grade cytological abnormalities, which often regress spontaneously without progressing to cervical cancer [10–12] Previous studies have shown that the long-term risk of cervical cancer in these women is relatively low. Nonetheless, referring them for colposcopy places a burden on healthcare resources, contributes to patient anxiety, and may lead to overtreatment.[13] In the context of rising healthcare costs and increasing pressure on the medical system, it is increasingly relevant to assess whether follow-up intensity for this subgroup can be safely reduced.

To date, the long-term risk of cervical cancer in HPV-positive women with low-grade cytological abnormalities has not been thoroughly evaluated. Given that eligible women are invited for screening every five years, it is crucial to assess whether these baseline abnormalities may progress to cervical cancer within that interval. Therefore, this study investigates the five-year incidence of cervical cancer among HPV-positive women with low-grade cervical abnormalities participating in the Dutch cervical cancer screening program.

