2. OBJECTIVES

Primary Objective:

To determine the five-year incidence of histologically confirmed cervical cancer in HPV-positive women with low-grade cytological abnormalities detected through the Dutch cervical cancer screening program.

Secondary Objectives:

- To assess time to cervical cancer diagnosis, all-cause mortality, type of examination at which the diagnosis was established and the histological characteristics of the carcinoma (subtype) in this population , within five years after enrollment.
- To assess cervical cancer risk stratified by histological diagnosis within three months of baseline abnormal cytology (\leq CIN 1 vs CIN 2+) and, for the \leq CIN 1 group, further stratified by cytology at 12-month follow-up (no or nondiagnostic cytology, \leq LSIL, HSIL +), with a follow-up period of five years and three months after enrollment.
- To perform a sub-analysis of women with a history of abnormal cytology or histology and assess their five-year cervical cancer risk.
- To evaluate the incidence of cervical cancer in women with stable NILM cytology after one year and compare it to the five-year incidence in women with low-grade cytological abnormalities.

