4. STUDY POPULATION

4.1 Population (base)

The study population consists of women who participated in the Dutch national cervical cancer screening program between January 2017 and December 2018. Eligible women were HPV-positive at baseline with either low-grade cytological abnormalities (ASC-US, AGC, LSIL) or stable NILM cytology one year after initial screening.

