4.2 Inclusion criteria

To be eligible to participate in this study, a participant must meet the following criteria:

- Women participating in the Dutch national cervical cancer screening program between January 2017 and December 2018.
- HPV-positive at baseline screening.
- One of the following cytology results:
 - ASC-US, AGC, or LSIL cytology according to the Bethesda system

or

- NILM cytology at one-year follow-up.

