6. STATISTICAL ANALYSIS

6.1 Primary study parameter(s)

The primary study parameter is the incidence of histologically confirmed cervical cancer within the five-year follow-up period. The cumulative incidence will be calculated as the number of new cases diagnosed divided by the total number of women included in the cohort. The incidence rate will also be calculated as the number of cervical cancer cases divided by the total follow-up time in person-years and expressed per 1,000 person-years.

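### The five-year total answers the primary objective, but no later risk is planned for the whole low-grade group, and the stable-NILM comparison is not like-for-like

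*Combined protocol and SAP*

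**What the plan says.** Section 6.1 defines the primary cumulative incidence as "the number of new cases diagnosed divided by the total number of women included in the cohort" and the rate as "the number of cervical cancer cases divided by the total follow-up time in person-years", per 1,000 person-years. Neither is split by time since the smear. Section 3 sets follow-up at five years and section 2 asks for five-year incidence, so measure and primary objective match.

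Section 1 says that women with abnormal cytology of any grade "are referred for colposcopy". It also says that "it is crucial to assess whether these baseline abnormalities may progress to cervical cancer within that interval".

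Three secondary outputs in section 6.2 bear on this:
- a line diagram of case numbers against time to diagnosis, with no statement that it is drawn by group;
- frequencies and percentages, by relevant group, of the kind of examination that led to the diagnosis;
- cumulative incidence and rates by histology in the first three months, ≤CIN 1 against CIN 2+ (section 2; written as >CIN I in section 5.1.2). Section 2 and the Summary give this analysis five years plus three months of follow-up, counted from enrollment.

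Section 2 also plans to estimate incidence in the stable-NILM group and "compare it to the five-year incidence in women with low-grade cytological abnormalities". The Summary's rationale explains the choice of benchmark: these are women "who are currently returned to the screening program". Section 4.1 describes them as having "stable NILM cytology one year after initial screening", and section 4.2 as having "NILM cytology at one-year follow-up". No section gives the start or length of their follow-up.

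**The concern.** The Summary wants to know whether follow-up intensity can safely be reduced. Two kinds of cancer inform that question differently. Cancers found at the referral work-up show what less immediate referral could delay. Cancers found afterwards show the risk left under current management. The planned total adds them together, so on its own it does not answer section 1's question about progression within the interval.

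The benchmark comparison inherits the problem. The low-grade side is counted from the result that triggers colposcopy. The NILM side is selected by a clear smear one year on and, as the plan describes the programme, is returned to screening. A low-grade figure above the NILM figure could therefore come from work-up detection alone. Within the strata, a CIN 2+ risk could be read as later risk after CIN 2+ when part of it is cancer already present at classification.

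**Working it through.** The documents give no cohort size, event count or expected rate, so there is no planned figure to reproduce. All shares and counts below are assumptions.

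**What the strata can recover.** With only ≤CIN 1 and CIN 2+, carcinoma found within three months can go only to CIN 2+. The ≤CIN 1 stratum therefore holds later cancers only. Women without histology in the window are not placed. Later risk for all low-grade women cannot be rebuilt from the two strata.

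**Inputs.** Horizon 60 months (section 3); window 3 months (section 2). Let π be the share of five-year cancers found within three months; a constant rate gives 3/60 = 5%. Let c be the share of later cancers that arise in CIN 2+. Person-time lost to death or diagnosis is ignored.

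**Formulas.**
- A: total over later cumulative incidence = 1/(1−π).
- B: pooled low-grade rate over NILM rate, with equal later rates and NILM time starting at the one-year smear = (1/5) ÷ ((1−π)/4.75) = 0.95/(1−π).
- C: as B, but with the NILM clock at baseline for five years. The first year is taken as event-free by selection, so the NILM rate falls to 4/5 of its true value, and the ratio is 0.95/(0.8(1−π)) = 1.1875/(1−π).
- D: CIN 2+ stratum risk over its later risk, if window cancers count = (π + (1−π)c) ÷ ((1−π)c) = 1 + π/((1−π)c).

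| π | A | B | C | D, c = 50% | D, c = 25% |
|---|---|---|---|---|---|
| 5% | 1.05 | 1.00 | 1.25 | 1.11 | 1.21 |
| 20% | 1.25 | 1.19 | 1.48 | 1.50 | 2.00 |
| 30% | 1.43 | 1.36 | 1.70 | 1.86 | 2.71 |
| 50% | 2.00 | 1.90 | 2.38 | 3.00 | 5.00 |

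Using 63 months in place of 60 for the strata changes little (3/63 = 4.8% against 5%).

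**Illustration.** Assume 10,000 women and 60 cancers. The planned total is 60/10,000 = 0.60%, or 60/50,000 = 1.20 per 1,000 person-years, whatever π is. At π = 50% the later risk is 30/9,970 = 0.30%, and the later rate is 30/(9,970 × 4.75) = 0.63 per 1,000.

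**Precision after splitting.** Assume 20 cancers and π = 20%. Exact Poisson 95% limits are:
- total, 20 cancers: 12.2 to 30.9 (0.61 to 1.54 times the estimate);
- later, 16 cancers: 9.1 to 26.0 (0.57 to 1.62 times);
- early, 4 cancers: 1.1 to 10.2 (0.27 to 2.56 times).

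**The case against.** The plan already shows part of the split. The examination-type table is given by group and is its most direct record of how cancers were found; the time diagram adds timing. A reader might infer that work-up and later cancers cannot be told apart at all, and that would go too far. But both outputs give counts, without a later denominator, person-years or rate, and the table may not separate the referral colposcopy from a later one.

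A reader might also infer that the CIN 2+ stratum is certainly circular. The documents do not settle that. Adding exactly the length of the classification window to follow-up suggests that a three-month landmark with five further years may be intended, in which case the circularity disappears. What stands is that follow-up is written as counted from enrollment and no rule removes window cancers from the outcome.

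For the decision whether to refer, the total from the low-grade result is a legitimate benchmark, because work-up cancers are the ones a change could delay. The later row has its own mismatch with NILM, since it follows colposcopy and any treatment. This stands, and it makes the later row a supplement, not a replacement.

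Finally, the absence of exclusion criteria might suggest that women with carcinoma before baseline inflate the count. The documents do not show that any are present, and the cumulative incidence in section 6.1 is limited to new cases.

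**Conclusion.** The point holds as a gap in what is pre-specified. The primary measure is valid for its objective; a reading that it is wrong or should be replaced has no support in the text. Three things are missing: a later risk and rate for the whole low-grade group, rules for window carcinoma and for women without histology, and a clock for the NILM group.

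The size cannot be derived from the documents. At π = 5% the pooling is negligible for the total (1.05) and absent from the NILM rate ratio (1.00), provided NILM time starts at the one-year smear. At assumed shares of 20% to 50% that ratio would read 1.19 to 1.90 with no difference in later rates. Starting the NILM clock at baseline multiplies it by a further 1.25. The CIN 2+ inflation, 1.11 to 5.00 over the assumed ranges, applies only if window cancers count as outcomes. The upper values illustrate sensitivity and are not predictions. The change should be made because the plan's safety reading and benchmark comparison depend on this distinction and the change is cheap.

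**What to change.** Keep the five-year total as primary, and add the following to sections 6.1 and 6.2:

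1. Time zero: the baseline abnormal smear for the low-grade group and the qualifying one-year smear for the NILM group. State the NILM horizon.
2. Two rows for the low-grade group: cancers within three months, and cancers after three months up to five years among women cancer-free at three months. Each has its own denominator, person-years and rate.
3. In the three-month strata, show carcinoma separately from CIN 2/3, count outcomes in the other strata only after three months, and add a category for women without histology in the window.
4. Give the NILM comparison as rates, because the windows differ in length, for both the total and the later row.
5. Describe the later row as a supplementary measure of risk after work-up under current management, not as pure progression. The plan gives no timing for the referral colposcopy, so some work-up cancers may be diagnosed after three months.

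The cost is a few lines of text, two table rows and two histology categories. Sections 5.1.2 and 5.1.3 already list the variables: histology at baseline and follow-up, and time to diagnosis. The downside is fewer events per row. In the example above the later row loses little precision, while the early row is imprecise and should be read as descriptive.

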6.2 Secondary study parameter(s)

Secondary study parameters include:

- Time-to-diagnosis of cervical cancer, which will be displayed in a line diagram with time on the y-axis and number of cases on the x-axis.
- All-cause mortality, type of examination at which the diagnosis was established, and histological subtype of cervical cancer, which will be summarized as frequencies and percentages for each relevant group.
- Cervical cancer incidence in women with stable NILM cytology after one-year follow-up, cervical cancer incidence in women with a history of abnormal cytology or histology, and risk stratification by histology within three months of baseline cytology and follow-up cytology at 12 months. For these parameters, cumulative incidence and incidence rates will be calculated.

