3. STUDY DESIGN

This retrospective cohort study includes women who participated in the Dutch national cervical cancer screening program between January 2017 and December 2018, with a follow-up period of five years.

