5.1.2 Secondary study parameters/endpoints

- Time to diagnosis of cervical cancer.
- All-cause mortality.
- Type of examination at which cervical cancer diagnosis was established.
- Histological characteristics of carcinoma (subtype).
- Cervical cancer incidence in women with stable NILM cytology after one year.
- Cervical cancer incidence in women with a history of abnormal cytology or histology.
- Cervical cancer risk stratified by histological diagnosis within three months of baseline abnormal cytology (\leq CIN I vs $>$ CIN I) and, for the \leq CIN I group, further stratified by cytology at 12-month follow-up (no or nondiagnostic cytology, \leq LSIL, $>$ LSIL).

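### Time to diagnosis is analysed only as raw case counts on reversed axes, so no planned output shows how cancer risk builds up within the five years

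*Combined protocol and SAP*

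**What the plan says.** Time to diagnosis is a secondary objective in Section 2 ("To assess time to cervical cancer diagnosis, all-cause mortality, type of examination at which the diagnosis was established"), set for the low-grade population over five years from enrolment. Section 5.1.2 lists it as a separate secondary endpoint ("Time to diagnosis of cervical cancer").

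Its analysis is the first bullet of Section 6.2, under which it will be "displayed in a line diagram with time on the y-axis and number of cases on the x-axis". The bullet contains nothing else.

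The third bullet of Section 6.2 ends: "For these parameters, cumulative incidence and incidence rates will be calculated". That sentence covers the stable-NILM group, the women with prior abnormalities and the histology and cytology strata. It does not cover time to diagnosis.

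For the primary endpoint, Section 6.1 defines cumulative incidence as the "number of new cases diagnosed divided by the total number of women included in the cohort" and the rate as the "number of cervical cancer cases divided by the total follow-up time in person-years and expressed per 1,000 person-years". Section 3 describes a cohort "with a follow-up period of five years". Section 6.3 undertakes to describe missing data but sets no censoring rule.

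**The concern.** The Summary asks whether follow-up of these women can safely be made less intensive, and Section 1 asks whether baseline abnormalities progress to cancer between screening rounds. Timing bears on both. Cancers found soon after referral for colposcopy may already have been present at the baseline sample, while cancers found in later years say more about progression. A five-year total cannot separate the two patterns.

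Time to diagnosis is the endpoint that could separate them, but its planned figure has three weaknesses:

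- **Axes.** With time on the vertical axis, slope means time per case. Rapid accrual then gives a shallow line, the opposite of how an incidence curve is read.
- **Type of count.** The text does not say whether cases are accumulated or counted per interval, and the two give different figures.
- **Denominator.** Case counts alone do not show how large the risk was by a given time.

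**Working it through.** The documents give no case count, cohort size or power calculation, so there is no stated figure to reproduce. All case and cohort numbers below are assumed for illustration. Only the five-year follow-up and the definitions in Section 6.1 come from the plan.

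**1. Axes, if counts are cumulative.** Assume 50 cases over 5 years, with a share diagnosed in the first 0.5 year and the rest spread evenly over the remaining 4.5 years. On the stated axes, slope = change in time / change in cases.

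| Early share | Cases early / later | Early slope (years per case) | Later slope (years per case) | Later / early |
|---|---|---|---|---|
| 40% | 20 / 30 | 0.5/20 = 0.025 | 4.5/30 = 0.15 | 6 |
| 60% | 30 / 20 | 0.5/30 = 0.017 | 4.5/20 = 0.225 | 13.5 |
| 80% | 40 / 10 | 0.5/40 = 0.0125 | 4.5/10 = 0.45 | 36 |

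With time on the horizontal axis, the same data accrue at 40, 60 or 80 cases per year early and at 6.7, 4.4 or 2.2 per year later. The early cluster is then the steep part.

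**2. Axes, if counts are per interval.** Take the 60% case in six-month intervals plotted at their midpoints. The first point lies at 30 cases and 0.25 year. The other nine lie at 20/9 = 2.2 cases, from 0.75 to 4.75 years. The early cluster is now one point far to the right, a sideways spike and not a flat segment.

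**3. Denominator.** A line ending at 50 cases is the same whatever the cohort size, but the five-year risk is not: 50/5,000 = 1.0%, 50/10,000 = 0.5% and 50/20,000 = 0.25%.

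**4. Whether Section 6.1 fills the gap.** Take 10,000 women with complete follow-up except for diagnosis, and 50 cases. Compare even accrual over five years with the 60%-early pattern.

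- The five-year proportion is 50/10,000 = 0.5% in both.
- Even accrual: cases lose on average 2.5 years, so person-years = 50,000 − 50 × 2.5 = 49,875. Rate = 50/49,875 × 1,000 = 1.003 per 1,000.
- Early accrual: 30 cases lose on average 4.75 years and 20 lose 2.25, so person-years = 50,000 − 142.5 − 45 = 49,812.5. Rate = 50/49,812.5 × 1,000 = 1.004 per 1,000.
- Risk at six months: 5/10,000 = 0.5 per 1,000 with even accrual, and 30/10,000 = 3.0 per 1,000 with early accrual.

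The two planned summaries are practically identical for patterns whose six-month risk differs sixfold.

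**5. Whether a reader could divide the counts by cohort size.** With a true five-year risk of 0.5% at constant hazard h = −ln(0.995)/5, and a share L lost at constant rate c = −ln(1−L)/5, the crude proportion is h/(h+c) × (1 − exp(−5(h+c))). For L = 0 it is 0.5%. For L = 5% it is 0.487% (2.5% too low in relative terms), and for L = 20% it is 0.448% (10.4% too low).

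**The case against.** The best defence is that this is a descriptive figure. No test or decision depends on it, swapping labelled axes changes no estimate, and the order may be a slip of wording. Time to diagnosis can also fairly mean a description of when cases occurred, and the plan does not call the figure a risk curve. If the count is cumulative and follow-up is nearly complete, dividing by cohort size recovers the crude cumulative incidence at every time point.

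Much of this stands. The axis order is a matter of presentation. Step 5 shows that simple rescaling does little harm when losses are small. But it needs a cumulative count, which the text does not promise, and near-complete follow-up, which the text does not establish. Correcting the axes would still leave a named endpoint without a denominator, a censoring rule or a risk at any intermediate time. That the study question turns on timing is an inference from the Summary and Section 1, though a reasonable one.

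Two stronger readings are tempting and should not be drawn:

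- **An early burst will appear as a flat line.** This holds only for cumulative counts; step 2 shows a different picture for per-interval counts.
- **Lines for groups of unequal size will be misread against each other.** Section 6.2 plans no such lines. The objective concerns the low-grade population, and the reference to each relevant group sits in the second bullet. The comparison with the stable-NILM group is one of incidence, for which Sections 6.1 and 6.2 do plan denominators.

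**Conclusion.** The point holds for this secondary endpoint. Its only planned analysis is a raw-count plot on reversed axes with the type of count left open, and no other planned output shows risk before five years. A cumulative incidence curve is a better method using essentially the same data, so this is more than a clerical correction to the axes.

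The consequence is moderate. A reader might infer that the study fails to report risk, or that its main result is biased. The documents support neither: five-year cumulative incidence and person-year rates are planned for the low-grade cohort and the other groups, and the way this figure is drawn does not touch them. The 6- to 36-fold slope ratios measure how a cumulative plot would look under assumed case splits, and are not a bias in any estimate. The absence of a denominator and of any intermediate risk follows from the text alone and needs no assumed numbers.

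**What to change.** Replace the first bullet of Section 6.2 with:

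> Time to diagnosis in the low-grade cohort will be shown as cumulative incidence of cervical cancer (per 1,000 women, y-axis) against time since the baseline screening sample (x-axis), as one minus Kaplan-Meier, or Aalen-Johansen with death as a competing event where death dates are available, censored at the end of available follow-up or five years, with numbers at risk and with estimates and 95% confidence intervals at 1, 2, 3, 4 and 5 years.

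The text is limited to the low-grade cohort because that is the population named in the objective. If other curves are added, their time origin must be set:

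- **Stable-NILM group:** start at the one-year cytology that defines inclusion.
- **Strata defined by 12-month cytology:** start at the 12-month landmark, among women still cancer-free. Starting at enrolment would sort women by information that arises later.

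The case-count plot may stay as a supplement, with time on the x-axis and a statement of whether counts are cumulative.

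The cost is one rewritten bullet and a little more analysis work. Diagnosis dates and follow-up times are already needed for the person-year rate in Section 6.1, and the competing-risk version is asked for only where death dates exist.

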5.1.3 Other study parameters

- Baseline characteristics such as age at inclusion.
- Cytology according to the Bethesda system and histology results at baseline and follow-up.
- HPV test results at baseline and follow-up.
- Relevant medical history, including prior abnormal cytology or histology.

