6.3 Other study parameters

Other study parameters include baseline characteristics such as age, which will be assessed for normality using the Shapiro-Wilk test. If normally distributed, this variable will be reported as means with standard deviation (SD). If non-normally distributed, it will be reported as medians with interquartile range (IQR). Cytology and histology results at baseline and follow-up, HPV test results, and relevant medical history will be summarized as frequencies and percentages for each relevant group. For the relevant medical history, the highest histology results will be presented. In case a patient has both cytological and histological results, histology will be prioritized. Pap scores will be converted to Bethesda system classifications using the KOPAC scores.[14] Missing data will be described, and analyses will include all available data.

All statistical analyses will be conducted using SPSS Statistics version 29 (IBM Corp., Armonk, NY, USA, 2025).

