7. ETHICAL CONSIDERATIONS

7.1 Regulation statement

This study will be conducted in accordance with the principles of the Declaration of Helsinki (2013 version) and in compliance with applicable Dutch laws and regulations. The study was approved by the scientific committee of Palga, the Dutch nationwide pathology databank in the Netherlands (approval number 2025-3). Ethical approval by a medical ethical committee was not required under Dutch law, as no patients were directly involved in the conduct of the research and only non-identifiable data were used.

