7.2 Recruitment and consent

No recruitment or informed consent procedures were applicable, as the study uses retrospectively collected, fully anonymized data from Palga.

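### Does reporting all-cause mortality from an anonymised pathology databank require the plan to name a vital-status source?

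*Combined protocol and SAP*

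**What the plan says.** All-cause mortality within five years of enrolment is a secondary objective (Summary; section 2, which lists "all-cause mortality, type of examination at which the diagnosis was established" together) and a secondary endpoint (section 5.1.2). Section 6.2 gives the summary: "All-cause mortality, type of examination at which the diagnosis was established, and histological subtype of cervical cancer, which will be summarized as frequencies and percentages". These are to be broken down by group, but the section states no denominator and does not define the groups.

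On the source, section 7.2 says "the study uses retrospectively collected, fully anonymized data from Palga", section 7.1 says "only non-identifiable data were used", and section 8.1 again names the pathology databank as the origin of the data. The Summary speaks more loosely of routinely collected screening-programme data but names no second database.

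Section 5.1.3 lists age, cytology, histology, HPV results and "Relevant medical history, including prior abnormal cytology or histology". It does not list vital status or date of death. The only missing-data rule is in section 6.3: "Missing data will be described, and analyses will include all available data".

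Section 6.1 defines two incidence measures. The cumulative incidence is cases "divided by the total number of women included in the cohort"; the rate is cases "divided by the total follow-up time in person-years".

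**The concern.** A pathology databank exists to hold tissue and cytology reports. A reader who sees it named as the only source, with the data fully anonymised and no register linkage described, will ask how deaths are to be counted. If they were visible only through pathology records, many deaths from other causes could go unseen, and the published percentage would not be all-cause mortality.

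Three things would then be at stake. The mortality figure could be too low by an unknown factor. Figures set side by side for different groups could differ because deaths are captured differently, not because mortality differs. And women who had died unrecorded would keep contributing follow-up time to the incidence rate in section 6.1.

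**Working it through.** The plan gives no mortality rate, event count or sample size, so there is no figure of its own to reproduce. The check has two parts.

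**1. What the text establishes**

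- *Is a source of deaths stated?* No. No section mentions a death or population register, a linkage, or a rule for unknown status.
- *Is the absence of such a source stated?* Also no. Nothing says what the databank records about death. Anonymised delivery does not exclude a link, because linking can be done before anonymisation.
- *Does section 5.1.3 show that deaths are not held?* No. It lists only the other parameters, and mortality is already in section 5.1.2. Date of cancer diagnosis and type of examination are also absent from section 5.1.3, although sections 5.1.2 and 6.2 need both.
- *Is a between-group mortality table planned?* Not clearly. Section 2 ties mortality to the low-grade cytology population. The objective on women with stable NILM cytology concerns cancer incidence only. The other two items in the same bullet of section 6.2 exist only for women with cancer.

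**2. What could follow, on assumed values**

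Let *m* be true five-year mortality and *c* the share of deaths captured. Neither is in the documents.

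*Reported mortality, all women in the denominator:* reported = *m* × *c*. With *m* = 1%:

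| *c* | reported |
|---|---|
| 10% | 0.10% |
| 25% | 0.25% |
| 50% | 0.50% |
| 100% | 1.00% |

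The shortfall is simply the assumed *c*.

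*Direction.* If only women with known status form the denominator, and a share *s* of survivors is known to be alive, reported = *mc* / (*mc* + (1 − *m*)*s*). This exceeds *m* whenever *c* > *s*. So the error could go either way, depending on a denominator that section 6.2 does not state.

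*Handling of unknowns.* Suppose 5% have recognised unknown status and mortality among the rest is 1%:

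- unknown counted as alive: 1% × 0.95 = 0.95%
- known only: 1.00%
- unknown counted as dead: 0.95% + 5% = 5.95%

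*Person-years.* With follow-up of 5 years and deaths spread evenly, true person-years per woman are 5(1 − *m*) + 2.5*m* = 5 − 2.5*m*. If no death is known, 5 is counted, and the overcount is 5/(5 − 2.5*m*) − 1:

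- *m* = 0.5%: 5/4.9875 − 1 = 0.25%
- *m* = 1%: 5/4.975 − 1 = 0.50%
- *m* = 3%: 5/4.925 − 1 = 1.52%

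In the last case the rate is multiplied by 4.925/5 = 0.985, so it is 1.5% too low. With partial capture and censoring at recorded deaths, the overcount is *m*(1 − *c*) × 2.5/(5 − 2.5*m*). At *m* = 1%, *c* = 5% this is 0.02375/4.975 = 0.48%. Section 6.1 does not itself state censoring at death.

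*Cumulative incidence.* Its denominator is all women included, so vital status does not enter it.

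**The case for a change.** The strongest case for a change is that the missing-data sentence in section 6.3 works only where missingness can be seen. Without a vital-status source, a woman with no death record may be alive or may be an unrecorded death. The gap would not show up as missing data, so it would not be described. The plan also gives a reason to expect unequal capture: women with abnormal cytology are referred for colposcopy, while those with stable NILM cytology return to routine screening, so their contact with pathology services probably differs. If 10% of deaths were captured in one group and 20% in another, at the same true 1%, a table would show 0.10% against 0.20%, a twofold difference that is not real.

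The first part stands as a point about section 6.3: that sentence does not supply a vital-status rule. But it leads to a wrong number only if no such source exists, and the documents do not settle that. The second part needs three unsupported steps: that deaths are seen only through pathology records, that capture differs by group, and that mortality is tabulated for those groups. The 10% and 20% are assumptions with no anchor in the plan. Withdrawing or renaming the endpoint would presuppose the very fact that is unknown.

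**Conclusion.** No change to the plan follows. The text does leave out where vital status comes from, the denominator and the handling of unknowns, but no stated rule or figure is shown to give a wrong result. This is missing detail on a descriptive secondary item, and whoever analyses the extract will know what it holds on deaths. Ordinary reporting covers it: give the source of deaths and its cut-off date, the denominator and the number with unknown status. If deaths turn out to be known only from pathology records, describe them as that and not as all-cause mortality.

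The size of any error in the mortality percentage cannot be found from the documents, and its sign depends on an unstated denominator. The primary cumulative incidence is unaffected. The person-year rate would be about 0.25% to 1.5% too low if no deaths were known, assuming five-year mortality of 0.5% to 3% and deaths spread evenly over follow-up. That is too small to affect the study's conclusions about cancer incidence.
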